Anhedonic adolescents will undergo a 12-week protocol of BA treatment. Neural (fMRI) and behavioral (PRT) measures will be assessed at pre- and post-treatment, and the EMA protocol will involve repeated assessment waves. We hypothesize that:

PARTNERS HUMAN RESEARCH COMMITTEE DETAILED PROTOCOL

- (a) Pre-treatment reward dysfunction (i.e., assessed via baseline fMRI, PRT and EMA), controlling for overall pre-treatment levels of depressive symptoms, will predict anhedonic (Snaith–Hamilton Pleasure Scale [SHAPS; Snaith et al., 1995]) symptom improvement over the course of BA.
- (b) Greater pre- to post-treatment normalization in neural (i.e., striatal and mPFC response to fMRI task) and behavioral (i.e., PRT performance) measures will be linked to greater anhedonic symptom improvement over the course of treatment.
- (c) Given emerging evidence of decreased cortico-striatal functional connectivity to reward-related stimuli in depression (Admon et al., 2015), we expect that BA will result in significant increases in cortico-striatal functional connectivity to rewarding stimuli from pre- to post-treatment.

(3) **Specific Aim 3:** Examine association between changes in neural reward circuitry and real-world positive affect and anhedonia: The EMA protocol will be implemented to acquire a more fine-grained and “real-world” assessment of changes in subjective positive affect (PA) and anhedonia, as well as the acquisition and use of BA skills, over the course of treatment. We hypothesize that:

- (a) Following BA, participants will report improvements in daily PA and anhedonia and increased use of BA skills.
- (b) Integrating across units of analyses (i.e., neural, behavioral and self-report), we expect that greater pre- to post-treatment normalization of striatal and mPFC response, cortico-striatal connectivity, as well as PRT performance will be associated with greater improvements in daily reports of PA and reduced anhedonia, as well as use of BA skills.

III. SUBJECT SELECTION

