which will allow for modeling the effects of repeated scans and practice effects (e.g., on the PRT). In addition, a smartphone-based EMA protocol will be implemented for both the anhedonic sample and healthy control sample involving repeated assessments of positive affect (PA) and anhedonia. The EMA protocol will use a smartphone app (*Beiwe*) already approved by both the Partners IRB (protocols 2015P001303; 2012P000890; 2015P000666) and Partners Research Information Security Office (RISO; see attached *RISO Approval for Beiwe EMA Application*). The latter app will be used for Android phones. For participants with iPhones, EMA data will be collected using the *Metricwire* app previously approved by RISO (see attached *RISO Approval for Metricwire EMA Application*) and the IRB (protocol 2015P001303). The schema outlining the assessment procedure is presented in **Table 1**.

Adolescent Cohort

General Inclusion Criteria:

- Both genders, any ethnicity
- Ages 13-18
- English as first language or English fluency
- Smartphone with iOS or Android platform (for EMA)
- *Healthy Control Sample:* Total SHAPS score = 0; *Anhedonic Sample:* Total SHAPS score ≥ 3 . The anhedonic sample must also meet criteria for elevated anhedonia on the K-SADS clinical interview (i.e., anhedonia item score > 1).

General Exclusion Criteria:

- History of head trauma with loss of consciousness for two minutes or more
- History of seizure disorder
- Serious or unstable medical illness, including cardiovascular, hepatic, renal, respiratory, endocrine, neurologic or hematologic disease
- Current use of cocaine or stimulant (e.g., amphetamine, cocaine, methamphetamine)
- Current use of dopaminergic drugs (including methylphenidate)
- Clinical or laboratory evidence of hypothyroidism
- Systemic medical or neurological illness that could impact fMRI measures of cerebral blood flow
- Color blindness
- Meet standard exclusion criteria for fMRI scanning (e.g. claustrophobia, cardiac pacemakers, neural pacemakers, surgically implanted metal devices, cochlear implants, metal braces, or other metal objects in their body);
- Positive urine pregnancy test
- Meets criteria for anorexia nervosa (DSM-5 diagnostic code: 307.1) or bulimia nervosa (DSM-5 diagnostic code: 307.51)

**PARTNERS HUMAN RESEARCH COMMITTEE
DETAILED PROTOCOL**

A. Anhedonic Adolescents: Anticipated enrollment = 65

Additional Exclusion Criteria:

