The adolescent portion of the study includes the following cohorts: (a) 35 anhedonic adolescents receiving BA and (b) 35 healthy control adolescents. The primary aim is to examine whether anhedonic and healthy adolescents differ on baseline neural (fMRI), behavioral (PRT) and self-report (EMA) measures of reward function, as well as whether behavioral and neural mechanisms prospectively predict and mediate symptom improvement among anhedonic adolescents receiving BA. Importantly, within the active treatment cohort, analyses will be conducted to determine if there are statistical differences in symptom, behavioral, and/or neural measurements between medicated and non-medicated depressed adolescents. Additional analyses will examine if there are statistical differences between participants on SSRIs versus participants on SSRIs plus other psychiatric medications.

Descriptive and Exploratory Analyses:

Descriptive statistics and exploratory graphical techniques, such as frequencies, means, medians, histograms, and box plots will be used to assess skewness and/or outliers in the data. Continuous/quantitative variables will be appropriately transformed when necessary, e.g., via log transformation for positively skewed distributions. For outcomes acquired during treatment, the analytical approach will address the type of outcome, as well as accommodating the within-individual correlation due to repeated assessments. In

PARTNERS HUMAN RESEARCH COMMITTEE DETAILED PROTOCOL

addition, the results will be assessed for sensitivity to dropouts or missing data. The primary analysis will be an intent-to-treat analysis, which includes all subjects. Of note, attempts will be made to continue assessing subjects even if they drop out of treatment.

Behavioral Variables:

For the PRT, the primary variable of interest will be *Reward Learning*, operationalized as the increase in response bias (RB) scores from Block 1 to Block 3 [$\Delta RB = RB(\text{Block 3}) - RB(\text{Block 1})$]. This variable was selected because it has been repeatedly linked to current and future anhedonic symptoms (Pizzagalli et al. 2005; 2008).

EMA-Derived Variables:

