For EMA, the primary variables of interest will be scores on the positive/negative affect and anhedonia items over the assessment periods. In addition, passive accelerometer data from the Beiwe app will provide data on amount of movement per day, which will be used to predict changes in self-reported affect and depressive symptoms. Given the longitudinal (i.e., repeated waves of EMA data) and hierarchical (i.e., assessment timepoints nested within individuals) structure of the data to be collected, Growth Curve Modeling (GCM) will be used to analyse EMA data (see *Statistics* below).

fMRI Processing:

fMRI: Gradient echo T2*-weighted echoplanar images will be acquired using the University of Minnesota multi-band BOLD EPI sequence (Feinberg et al., 2010; Moeller et al., 2010; Xu et al., 2013), which achieves excellent temporal and spatial resolution (TR/TE: 1300/35ms; FOV: 224 mm; matrix: 64X64; 78 slices; in-plane resolution: 2mm; voxels 2 x 2 x 2mm, multiband factor of 6). The EPI acquisition will use prospective motion correction to minimize the effects of subject motion. Analyses will be conducted using SPM8 and FreeSurfer (Fischl et al., 2002). Pre-processing will include motion/slice-time correction, removal of slow linear trends, intensity normalization, and spatial smoothing (6-mm).

Statistics:

GCM will be used to test the hypothesis that pretreatment reward dysfunction (fMRI, PRT, EMA), controlling for overall pretreatment levels of depressive symptoms (BDI), will predict anhedonic (SHAPS) symptom improvement over the course of BA. Given our multimodal assessment of reward system dysfunction, pretreatment predictors will include: (1) self-reported anhedonia (i.e., baseline EMA), 2) neural (i.e., striatal and mPFC) response to monetary rewards on the fMRI reward task and (3) reward learning scores on the PRT. The dependent variable in these analyses will be anhedonic (SHAPS) symptom improvement. GCM is well-suited for handling repeated symptom assessments over time (i.e., session-to-session SHAPS scores), as well as accommodating missing observations in longitudinal datasets.

With regards to fMRI analyses, data will be analyzed using an ROI approach to evaluate *a priori* hypotheses, followed by a whole-brain analysis to test regional specificity of findings. In the first approach, regression coefficients (“beta weights”) will be extracted

PARTNERS HUMAN RESEARCH COMMITTEE DETAILED PROTOCOL

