from ROIs obtained from FreeSurfer's parcellation. Informed by the relevant literature, and consistent with reward circuitry hypotheses, ROIs will include striatal (NAc, putamen, caudate) and cortical (mPFC) regions. For each subject and ROI, results of one-sample *t* tests (reward feedback > baseline) will be extracted for inclusion in growth models estimating SHAPS improvement. In the second approach, whole-brain analyses will be run predicting SHAPS improvement. For these analyses, each subject's data will first be re-sampled into Talairach space and random effects analyses will be conducted.

GCM will also be implemented to test the hypothesis that greater pre- to post-treatment normalization in neural (i.e., striatal and mPFC response to fMRI task) and behavioral (i.e., reward learning on PRT) responsiveness will be associated with greater anhedonic symptom improvement over the course of BA treatment. For fMRI analyses, for each of the above ROIs and consistent with prior work (Dichter et al., 2009), a *Group* (AH, HC) X *Time* (Pre-, Post-treatment) X *Condition* (Monetary Gains, Monetary Losses) interaction will be tested. For significant ROIs, pre- to post-treatment change in ROI activation will be entered as predictor variables in growth models estimating SHAPS improvement. For the behavioral (PRT) analyses, a *Group* (AH, HC) X *Time* (Pre-, Post-treatment) interaction will be tested, followed by correlations between reward learning scores and anhedonic (SHAPS) symptom change.

VII. RISKS AND DISCOMFORTS

(a) *Privacy*. A potential risk is a breach of confidentiality. To protect against the loss of confidentiality, we will keep all study data locked in a separate file, coded by a unique study code number (with names and other personal identifying information kept separately). Further, the consent and assent forms will clearly inform subjects of the limits of confidentiality, including the circumstances in which confidentiality may be breached such as in cases of suspected child abuse or neglect and dangerousness to self or others.

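### The Aim 2(a) growth models adjust for depression but not for starting SHAPS, so a reward measure that only tracks initial anhedonia can be read as predicting improvement in its own right

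*Combined protocol and SAP*

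**What the plan says.** Section II, Specific Aim 2(a), states the hypothesis as "controlling for overall pre-treatment levels of depressive symptoms", with SHAPS improvement during BA as the outcome. The Statistics part of section VI repeats this and names the depression scale: "controlling for overall pretreatment levels of depressive symptoms (BDI), will predict anhedonic (SHAPS) symptom improvement over the course of BA". It adds: "The dependent variable in these analyses will be anhedonic (SHAPS) symptom improvement". The predictors are "self-reported anhedonia (i.e., baseline EMA"), striatal and mPFC response on the fMRI reward task, and PRT reward learning.

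The model is a growth curve: "GCM is well-suited for handling repeated symptom assessments over time (i.e., session-to-session SHAPS scores"). Time coding and random effects are not given, nor whether the slope is regressed on the intercept. For the imaging predictors, ROI values "will be extracted for inclusion in growth models estimating SHAPS improvement", with no further covariate; the whole-brain analysis names none either.

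Table 1 schedules SHAPS at Pre I, Pre II, sessions 1 to 12 and Post, which makes 15 occasions, two of them before session 1. The Sample Size part gives "a) 35 anhedonic adolescents receiving BA and (b) 35 healthy control adolescents", while section III gives "A. Anhedonic Adolescents: Anticipated enrollment = 65". No power calculation, significance level or SHAPS standard deviation is stated.

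**The concern.** Adolescents who start with higher SHAPS have further to fall, so a negative correlation between starting level and slope is plausible, although the documents do not report one. Baseline EMA anhedonia measures the same construct as SHAPS. PRT reward learning was chosen partly for its reported link to current anhedonia. Any predictor that correlates with starting SHAPS inherits part of the relation between starting SHAPS and slope.

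The growth model does not remove this. A random intercept, even with a free intercept-slope covariance, does not make the predictor-by-time term conditional on starting level. That requires starting SHAPS by time in the model, or the latent slope regressed on the latent intercept. Total depression is only a partial proxy for starting anhedonia.

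At stake is what a positive Aim 2(a) result means. As planned, it could not separate information in the reward measure from information already contained in the entry SHAPS score.

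**Working it through.** The plan has no figure to reproduce, so the check is a closed form followed by simulation.

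**Inputs from the documents.** Depression is the only covariate (section II, Aim 2(a); section VI, Statistics). n = 35 (section VI, Sample Size), with 65 as an alternative (section III). SHAPS is measured at two visits before session 1 (Table 1).

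**Assumed inputs.** Two-sided 5% level; complete data. Predictor-to-start correlation ρ = 0.3 or 0.5; start-to-slope correlation r_IS = -0.3, -0.5 or -0.7; depression-to-start correlation r_D = 0.4. The predictor has no link to the slope except through starting level.

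**Closed form.** The correlation between predictor and true slope, given depression, is

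ρ·r_IS·(1 − r_D²) / √[(1 − ρ²r_D²)(1 − r_IS²r_D²)].

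- ρ = 0.3, r_IS = -0.3: -0.09 × 0.84 / 0.9856 = -0.08.
- ρ = 0.5, r_IS = -0.7: -0.35 × 0.84 / √(0.96 × 0.9216) = -0.294 / 0.9406 = -0.31.

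It is zero only if ρ = 0, r_IS = 0, or depression is a perfect proxy for starting level (|r_D| = 1).

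**Simulation with the correlations holding within the enrolled sample.** 4,000 replicates, person-level slopes from 14 assessments, residual SD 0.6, n = 35, depression as the only covariate. Rejection rates:

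| ρ | r_IS = -0.3 | r_IS = -0.5 | r_IS = -0.7 |
|---|---|---|---|
| 0.3 | 6.8% | 9.4% | 15.3% |
| 0.5 | 9.5% | 19.7% | 35.6% |

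A repeat gave about 5-34% over the same grid. Adding one pre-treatment SHAPS brings the range to 4.9-8.6%; adding the mean of two brings it to 4.6-7.2%. At n = 65 and r_IS = -0.5, the rates are 14.5% (ρ = 0.3) and 34.8% (ρ = 0.5), falling to 5.5% and 5.6% with the mean of two. A larger sample therefore makes the unadjusted problem worse.

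**Simulation with the correlations describing an unselected population.** Selecting on an error-prone Pre I score narrows the range of starting SHAPS in the enrolled sample. At n = 35, with the series from session 1, the ρ = 0.5, r_IS = -0.7 cell falls from about 35% to 15-17%. The ρ = 0.5, r_IS = -0.5 cell falls from 19% to 9-10%, and the ρ = 0.3 cells to 5-9%. Overall the range is about 5-16%.

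**Selection with no start-to-slope correlation.** With r_IS = 0, selection on the noisy Pre I score and ρ from 0.3 to 0.7, rejection was 4.4-5.9%, whether the series began at Pre I or at session 1.

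**Does the growth-model intercept help?** With n = 35, ρ = 0.6, r_IS = -0.6 and r_D = 0.5, a mixed model with random intercept and slope and free covariance rejected in 37% of 300 fits, against 34% from the slope regression. Some fits gave convergence or boundary warnings, so this is a rough check. Conditioning on the true starting level gave about 5%.

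**The case against.** The strongest objection concerns the question being asked. Aim 2(a) asks whether reward dysfunction predicts improvement given overall depression, and EMA anhedonia is one of the plan's own measures of that dysfunction. A marker of initial anhedonia that predicts improvement is then a true prognostic predictor. This stands: the rates above are error rates only against the null of no effect beyond starting SHAPS, and the adjusted analysis answers an added-value question. It belongs beside the planned analysis and does not replace it.

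A reader might also infer that recruiting on SHAPS of 3 or more creates the association through regression to the mean. The documents do not support that. The predictors are separate measurements, and if their errors are independent of the error in the qualifying score, noise in that score is not credited to them. The run with no start-to-slope correlation stayed at about the nominal rate.

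Nor do the documents show that every predictor is equally exposed. No figure shows how closely ROI response or PRT learning tracks starting SHAPS.

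Finally, the reference to session-to-session scores may mean that the outcome series already starts at session 1. If so, that part of the fix only needs to be stated.

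**Conclusion.** The point holds in a conditional form. Starting SHAPS is missing from the covariates, the depression adjustment replaces it only in part, and the growth-model intercept does not supply it. Whether this matters depends on a relation between starting SHAPS and slope and on how closely each predictor tracks starting SHAPS; the documents give neither. Over the assumed ranges at n = 35, the rate is about 5-36% if the correlations hold within the enrolled sample and about 5-16% if they describe an unselected population. It is nominal if either is zero. The simulations assume complete data, and floor effects were not examined.

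A related point needs reconciling. The covariate is named as the BDI, but the documents list the BDI-II only as a parent's self-report; the adolescent depression measures are the CES-D, MFQ and CDRS-R. A reader might infer that a parent's own score is to be used, leaving no useful adjustment. The aim's wording about overall depressive symptoms does not support that reading, but the scale should be named.

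**What to change.** In the Aim 2(a) models, add the mean of Pre I and Pre II SHAPS and its interaction with time, and state that the outcome series starts at session 1 (13 occasions: 12 sessions and Post). Regressing the latent slope on the latent intercept is an acceptable alternative; if that is already intended, one sentence should say so. Report each predictor with and without the adjustment, and claim that a reward measure predicts improvement beyond initial anhedonia only from the adjusted model. Name the adolescent depression scale used as covariate.

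The cost is two fixed effects and some loss of power for predictors correlated with starting SHAPS, most of all EMA anhedonia. The SHAPS assessments are already scheduled, so no visit or questionnaire is added.

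### The whole-brain step is meant to test regional specificity but compares no region with another: it can count against specificity, not establish it

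*Combined protocol and SAP*

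**What the plan says.** The fMRI plan is in Section VI, under Statistics. ROI analyses come first, "followed by a whole-brain analysis to test regional specificity of findings". The a priori regions are listed there: "ROIs will include striatal (NAc, putamen, caudate) and cortical (mPFC) regions". A reward-feedback-versus-baseline estimate from each ROI enters growth models of SHAPS improvement.

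The whole-brain step is described in two sentences. "In the second approach, whole-brain analyses will be run predicting SHAPS improvement", and each adolescent's data are "re-sampled into Talairach space and random effects analyses will be conducted".

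For pre- to post-treatment change, a Group x Time x Condition interaction is tested "for each of the above ROIs and consistent with prior work", one region at a time. Then: "For significant ROIs, pre- to post-treatment change in ROI activation will be entered as predictor variables".

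The plan contains no region factor, no comparison of coefficients between regions and no control region. It also gives no whole-brain threshold, no multiplicity correction and no rule for concluding that a finding is regionally specific.

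**The concern.** The stated purpose and the described method do not match. Regional specificity is a statement about a difference: the association with improvement is stronger in reward regions than somewhere else. A whole-brain regression on SHAPS improvement asks at each location whether the association differs from zero. It does not ask whether two associations differ from each other.

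The step is informative in one direction only. Associations outside the ROIs would be evidence against specificity. A lack of them could mean that the association is absent there, or that the study had too little power to detect it. With about 35 treated adolescents the second explanation is hard to exclude. At stake is whether a report could describe an ROI association as particular to reward circuitry when one or a few other regions share it equally.

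**Working it through.** **Inputs from the plan.** The Sample Size paragraph gives "35 anhedonic adolescents receiving BA". Section III.A gives "Anticipated enrollment = 65" for the same cohort, so both sizes are shown. No alpha, threshold, effect size or power is stated for these analyses, so there is no figure of the plan's to reproduce.

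**Assumptions, for illustration only.** The ROI is tested at two-sided 0.05. The other region is judged at an uncorrected 0.001 or at 0.05. True correlations with improvement are 0.3 to 0.5, and inter-region correlations 0.2 to 0.7. Data are normal, with one improvement score per adolescent in place of a full growth model.

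**Step 1: power for one region.** Power ≈ Φ(atanh(r)·√(n−3) − z). For r = 0.4 and n = 35, atanh(0.4)·√32 = 0.4236 × 5.657 = 2.397.
- At 0.05: Φ(2.397 − 1.960) = 67%.
- At 0.001: Φ(2.397 − 3.291) = 19%.

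**Step 2: equal true association in both regions.** Simulation, 40,000 replicates, n = 35, inter-region correlation 0.2 to 0.7:

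| True r, both regions | Power at 0.05 | Power at 0.001 | ROI p<0.05, other not p<0.001 | ROI p<0.05, other not p<0.05 |
|---|---|---|---|---|
| 0.3 | 42% | 6% | 37–39% | 13–22% |
| 0.4 | 67% | 19% | 51–55% | 12–20% |
| 0.5 | 87% | 43% | 47–51% | 6–10% |

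The chance that the other region misses, given a significant ROI, is the joint proportion divided by the proportion with a significant ROI. At r = 0.4 and inter-region correlation 0.5 this is 0.526 / 0.680 = 77%. At inter-region correlation 0.3 it is about 80%.

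With both regions at 0.05, r = 0.4 and inter-region correlation 0.3 to 0.5, exactly one region is significant in 31 to 37% of studies. Only half of these have the ROI as the significant one: 15.5 to 18.5%, or about 16 to 18%.

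**Step 3: n = 65.** At r = 0.4 and inter-region correlation 0.5, the conditional miss rate at 0.001 is 0.418 / 0.917 = 46%. With both at 0.05, the ROI alone is significant in about 6%.

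**Step 4: a direct test.** Williams' t for two dependent correlations, two-sided 0.05, n = 35:
- Equal associations: a false difference in 4.8 to 5.0% of studies, counting both directions.
- True 0.4 versus 0: power 48%, 70% and 91% at inter-region correlations of 0.2, 0.5 and 0.7.
- True 0.4 versus 0.2: power 16%, 23% and 35%.

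A contrast of standardised slopes with both regions in one model has the same null hypothesis. With correlations r₁ and r₂ and inter-region correlation ρ, b₁ − b₂ = (r₁ − r₂)/(1 − ρ), which is zero exactly when r₁ = r₂.

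**Step 5: a brain-wide correlate.** Suppose many regions share r = 0.4 (n = 35, inter-region correlation 0.3 to 0.5). Given a significant ROI, all of 20 other regions miss 0.001 in 9 to 15% of cases, and all of 50 in 2 to 6%. At r = 0.3 the figures are roughly a third and a fifth. The numbers of regions are assumptions.

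**The case against.** The strongest reply is that the plan promises less than a critic may read into it.

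- A reader might infer that specificity will be concluded from significance in the ROIs and its absence elsewhere. The documents state no such rule and no threshold. A whole-brain search is a legitimate one-way check.
- A reader might infer that the study's mechanistic hypotheses depend on specificity. Section II does not support that: its hypotheses are that reward measures differ between groups, predict improvement and change with it. None says that these regions differ from others.
- A reader might infer that a global correlate, such as arousal or scan quality, would pass as reward-specific. Step 5 points the other way at r = 0.4, where such a correlate would usually show somewhere on the map.
- The 77 to 80% figure pairs 0.05 in the ROI with an assumed 0.001 elsewhere. On a single map with one threshold, an ROI that passed 0.05 would itself miss 0.001 in about 74% of cases at r = 0.4.
- At n = 65 the figures fall, and with both regions at 0.05 the misleading pattern occurs in only about 6%.

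All of this stands, and it limits the point. It does not supply the missing comparison. The plan uses the word test, and the analysis it describes cannot carry out that test in the direction that would support specificity.

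**Conclusion.** The concern holds in a limited form. The described whole-brain analysis cannot establish regional specificity because it compares no regions. This follows from the text and depends on no assumed number.

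The practical risk is an association shared with one or a few other regions. Under equal true associations of 0.4 at n = 35, a significant ROI is accompanied by a miss at 0.001 in one such region about 77 to 80% of the time. With equal thresholds of 0.05, the ROI alone is significant in about 16 to 18% of studies, against about 5% false differences from a direct test. These figures rest on assumed effect sizes, thresholds and inter-region correlations, and they shrink at n = 65.

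The point affects how a secondary imaging result may be described. It does not undermine the ROI hypotheses, and the documents do not show that an unsupported specificity claim will be made.

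**What to change.** In Section VI (Statistics), relabel the whole-brain step as an exploratory search outside the ROIs. State its threshold and multiplicity correction, and say that no specificity claim will be made from a null map.

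If specificity is to be claimed, pre-specify a direct comparison:
- Name one non-reward region from the same FreeSurfer parcellation, and the reward ROI it will be compared with.
- Extract the same contrast from both and standardise both predictors, so that the slopes do not depend on each region's signal variance.
- Enter both predictor x time terms in one SHAPS growth model. Each adolescent has a single SHAPS trajectory, so the test is a contrast between these two slopes, not an interaction with a region factor.
- Report the difference between the slopes with its confidence interval. Claim specificity, relative to that region only, if the interval excludes zero on the side of the stronger reward-region slope.

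The cost is a change of wording and one extra model on scans already planned. The drawback is power. At n = 35 it is about 48 to 91% for true correlations of 0.4 versus 0, and 16 to 35% for 0.4 versus 0.2, under the assumed inter-region correlations. Specificity therefore becomes harder to claim. If that power is judged too low, the relabelling alone is enough.
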